# Implementing Family-Based Treatment for Adolescent Anorexia Nervosa for Providers in Private Practice: A Feasibility Study

Study Protocol

NCT04428580

June 9, 2020

We will employ the same recruitment strategy that was successful in our initial study and advertise throughout the United States (US) on the Academy for Eating Disorders (AED) websites, Eating Disorder Research Society (EDRS) listserve, and the National Eating Disorder Association (NEDA) listserve. In addition, we will use Facebook and Twitter advertisements to augment these approaches.

Therapists will be trained in one of two ways for this study: 1) online training x 3 months, followed by expert supervision for 3 months; or 2) recorded webinar training provided in 12 1-hour webinar lectures provided weekly, followed by expert supervision for 3 months. UCSF, listed as a collaborating institute, will aid in training and supervising the participating therapists in one of these two arms of Family-based Treatment training (see description of research activities at UCSF below).

Therapists are eligible to participate if they have completed a masters or doctoral training in their field (psychology, psychiatry, family therapy, social work), are licensed in their respective state, have no reports of malpractice or loss of privileges at relevant clinical institutions, have computer/web access for online training and assessments and no previous 2-day in-person workshop training in FBT, and submit baseline data on weight gain from week 1-4 from a previously treated adolescent with AN they have treated in the last 6 months or alternatively one that they treat within 3 months of the initial screening before starting the training. Therapists who have had previous training in FBT are not eligible to be randomized.

Therapists will complete an online screen. If they appear to be eligible, an online consent form will be triggered (waiver of documentation included on the application). If they do consent, they will be asked to complete online questionnaires that will amount to be the baseline assessment prior to randomization. Demographic and practice characteristics of all therapists (age, gender, ethnicity, race, months of experience treating eating disorders, specialized trainings, practice setting, payments accepted), self- report of fidelity, knowledge of FBT, skills of FBT using responses to role played videotapes, and expert ratings of fidelity will be collected. The total assessment burden for therapists will be about one hour to an hour and a half for the entire screen, consent, and baseline assessment.

Once this is complete the research team will review the assessment and double check eligibility before randomizing the participant to either arm of training. The research team will then reach out to the therapist to inform them of which arm of training they were randomized to and go over again what that entails as well as get them set up with either:

1) Online training which consists of 10 lectures that are self-paced with a maximum of three months to complete with each lecture bundle comprising of 5- 8 short (about 4 minutes in length), didactic videos that discuss the treatment model and provide mock therapy session video clips (modeling FBT with a typical adolescent AN case), as well as supplementary readings and videotaped role- plays. Enrollees complete each lecture bundle and complete the assignments as they move through the training at their own pace, but to have completed all within the 3-month time frame.

2) Webinar training which consists of 1-hour weekly webinar lectures that essentially is the FBT training that is conducted in person, just recorded. There will be lectures discussing the scientific evidence supporting FBT, how therapists set up treatment for FBT, main interventions used in FBT during each phase, and recorded role-plays illustrating interventions throughout the 3 phases. Enrollees watch each webinar video as it is released weekly over a 12 week (3 month period).

When the training is completed, therapists will proceed to schedule post- online supervision for a minimum of 1 case and a maximum of 2 cases over the course of 3 months with one of two clinicians at UCSF. At the 4 week treatment mark for each case, therapists will complete a self-report on FBT fidelity to key components and patient weight change. Therapist video skill assessments related to key components will take place at baseline and at the end of online ET-FBT and end of supervision. Once the therapist completes a minimum of one case, the therapist will receive CE credit and a certificate of completion of FBT training. Therapists who enter the online training protocol will be compensated for their time for the completion of all assessments (\$100 for each assessment point).

UCSF's role in research activities are as such: Two UCSF clinicians will be responsible for conducting individual work with each therapist participant weekly for 1 hour per week for 12 weeks during the supervision timepoint of the study. They will use the published supervision manual for FBT (Forsberg et. al) published by Guilford. They will rate fidelity using a therapist version of self-report (described below) and will rate the recorded responses to the

clinical vignettes (described below). They will have access to all of the fidelity assessments (the self-reports and the vignettes all outline below) in order to complete these ratings. Access will be through RedCap in order to make sure the data they receive is secure and HIPAA compliant in accordance with Stanford's IT recommendations. They will also know the patient weight change data (solely session 1 through 4 weights and dates taken no patient PHI will be collected in the study) as they need this information to teach the therapist using supervision.

Therapists will complete the following measures/assessments:

Demographic and professional survey: This is a basic demographics questionnaire asking for age, race, gender, geographic location (City and State), specialty (psychology, psychiatry, social work), treatment setting (private practice, group private practice, full or part-time); specialty training in anorexia nervosa, experience treating anorexia nervosa (years), numbers of adolescents with AN treated in the last two years, willingness to pay for this training. This measure will take approximately 10 minutes to complete and is completed only at baseline (BL). This measure will be used to examine possible predictors (candidate-moderators) for fidelity and patient outcome (Aim 4).

The therapist version of Parents versus Anorexia Nervosa Scale(PVAN): This is measure of therapist self-efficacy specific to key components knowledge and skill in FBT. We use this measure as a learning tool in ET-FBT. It takes 5 minutes to complete. This measure will be completed at BL, ~3 months (end of online training-EOT), and end of supervision (EOS) ~6 months. This measure will be used as a possible predictor (candidate moderator) for fidelity and patient outcome (Aim 4).

Evidence-based Practice Attitude Scale-36 (EBPAS-36): This is a brief version of EBPAS-50 and is a measure of therapist attitudes about evidence-based practice. It has sound psychometric properties and takes about 10 minutes to complete. This measure will be used as a possible predictor (candidate moderator) for fidelity and patient outcome and will be given at BL only (Aim 4).

Motivation for training in FBT: This is a new measure asking for therapist to choose one of the following reasons for seeking training in FBT: belief that this is the best approach; customer demand; curiosity about the approach; increased income; professional development. Therapists may choose as many reasons as they wish but will rank those they choose. This measure will take 5 minutes to complete. This measure will be used as a possible predictor (candidate moderator) for fidelity and patient outcome (Aim 4).

Treatment Outcome Measures:

Weight change in patients treated pre and post-training: Weight change from sessions 1 to 4 will be collected on one adolescent patient with AN treated pre-training (baseline eligibility) and post online ET-FBT per participating therapist during supervision or within 3 months following completion of supervision. No patient identifying information will be collected. This will take 5 minutes to complete. This measure will be used as the main outcome for treatment (patient outcome) efficacy (Aim 2).

Key component skills: Therapists will be asked to view mock therapy session video clips and play the role of the therapist. These clinical videotapes are actors playing families using a script and usually lasting less than three minutes. The therapist in training watches the video and records their verbal intervention response to the clinical scene. The specific skills assessed are related to how effectively the therapist used externalization or agnosticism (as appropriate clinically) and will be scored by expert clinicians using standardized coding. This was the approach used in our preliminary study. This measure will be completed at BL, ~3 months (end of online training-EOT), and end of supervision (EOS) ~6 months. This is a measure of fidelity and change will be correlated with patient weight change outcome (Aim 3) for target validation.

Key component knowledge: This is a brief 10 question multiple choice measure of knowledge of key components of FBT that was used in our preliminary study. These will be conducted at BL, ~3 months (end of online training-EOT), and end of supervision (EOS) ~6 months. This is a measure of fidelity and change will be correlated with patient weight change outcome (Aim 3) for target validation.

Consultation Questions: The brief 8 questions ask participants about their experience with supervision in the research study. This measure will be administrated at ~3 months (end of training-EOT), and end of supervision (EOS) ~ 6 months.

**Fidelity to FBT Self-Report:** This is a new measure that has been piloted at the two study sites and found acceptable to therapists to use as a brief measure of self- reported fidelity to key component of FBT during the first 4 sessions. It consists of 8 multiple choice questions and takes approximately 5 minutes to complete. This will be conducted at BL, end of training (~ 3 months), and end of supervision (~6 months). This is a measure of fidelity and change will be correlated with patient weight change outcome (Aim 3) for target validation.

**Supervisor reported fidelity to key components of FBT:** Using a published coding frame that was used in our previous studies, supervisors will rate therapists during supervision on their fidelity to FBT during the first 4 sessions. This will be completed only at the end of supervision by therapy supervisors. This measure is a measure of fidelity and change will be correlated with patient weight change outcome (Aim 3) for target validation.

**Working Alliance Inventory:** This is a 12-item Likert measure derived from the original 36 item version with satisfactory psychometrics. The therapist will be asked to complete the measure as it relates to the patient for whom post- training weight change is provided. It will take 5 minutes for the therapist to complete. These will be conducted at BL, end of training (~ 3 months), and end of supervision (~6 months). This is a measure of fidelity and change will be correlated with patient weight change outcome (Aim 3) for target validation.

For the purpose of this study adverse events will be defined as “unanticipated problems involving risk to the study participant.” A serious adverse event will be defined as “any untoward occurrence that results in death; is life-threatening; or creates persistent or significant disability.” All such events will be immediately reported to the IRB and DSMB. These events will be reviewed by the Data and Safety Monitoring Board (DSMB) at their regular meeting, however, deaths and suicide attempts will be immediately reported to the DSMB and IRB.

The initial reporting of adverse events (of any kind) will take place with the study staff consulting with the PI. The PI will then decide whether the event is of such a severity that requires discontinuation of a particular training, and whether the participant should remain in the study or be withdrawn. All study withdrawals together with a detailed explanation of the withdrawal will be reported to the DSMB.

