In **Aim 1**, we will first examine how well we can retain clinicians in our study. We will consider retaining 50% by end of study (6 months from the baseline) as neither success nor failure and at least 65% as successful retention. We will employ simple one-sample chi-square test (2-tailed, alpha=.05) comparing the sample retention to 50%. We will then examine whether therapist fidelity and competency in implementing FBT significantly improves from pre training to post training. For this investigation, we will employ longitudinal mixed effects modeling, which enables us to fully utilize outcome data repeatedly measured for most clinicians (3 assessments: 0 (pre), 3 and 6 month). Data points that are missing due to clinician attrition or intermittent dropout will be handled assuming that data are missing at random conditional on observed information. In this procedure, all available cases including the ones with missing information will be included in the analyses. We believe such missing data assumption is reasonable given that we will include variables (e.g., clinician fidelity/competency) supposedly related to attrition in our mixed effects modeling. Nonetheless, as a way of sensitivity analysis, we will conduct mixed effects analyses with and without including other possible predictors of attrition, which we believe is important to support the validity of our study findings as we expect a considerable level of attrition. For estimation of mixed effect models, we will employ maximum likelihood (ML) estimation embedded in the Mplus program.

In **Aim 2**, using the same mixed effects modeling approach, we will examine whether the patient outcome (weight gain) significantly improves from pre to post training.

In **Aim 3**, we will examine the relationship between the changes in clinician outcomes (fidelity/competency) and the change in patient outcome (weight gain). This will be investigated in the latent variable modeling framework, by formally relating the parallel longitudinal processes (esp. by correlating the slopes) of patient and clinician outcomes. This investigation is of particular

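### No rule fixes which patient supplies the pre-training or the post-training weight gain, so the uncontrolled pre-to-post test in Aim 2 is open to case selection

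*Protocol*

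**What the plan says.** **Before training.** The therapist eligibility paragraph of the Protocol requires each therapist to "submit baseline data on weight gain from week 1-4 from a previously treated adolescent with AN they have treated in the last 6 months". It then allows a second route for the same requirement: "or alternatively one that they treat within 3 months of the initial screening before starting the training". Under *Weight change in patients treated pre and post-training*, the Protocol then takes a single case per therapist as the pre-training value: "Weight change from sessions 1 to 4 will be collected on one adolescent patient with AN treated pre-training (baseline eligibility").

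**After training.** The same item accepts a case treated "post online ET-FBT per participating therapist during supervision or within 3 months following completion of supervision". The paragraph on supervision provides for "a minimum of 1 case and a maximum of 2 cases over the course of 3 months", and at four weeks into each case "therapists will complete a self-report on FBT fidelity to key components and patient weight change".

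**Use.** The Protocol says of this item: "This measure will be used as the main outcome for treatment (patient outcome) efficacy (Aim 2"). For Aim 2 the SAP's Data Analytic Plan states only that "we will examine whether the patient outcome (weight gain) significantly improves from pre to post training", with the mixed-model approach of Aim 1. The SAP's list of aims also names a comparison between the randomized groups.

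**Not stated anywhere.** There is no rule for choosing among several patients at either time point, whether most recent, consecutive, random or picked by staff. There is no log of eligible cases. Staff double-check eligibility before randomization, but no check on which case was submitted is described. The one planned sensitivity analysis concerns attrition.

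**The concern.** A therapist with several eligible past patients knows how each gained weight when deciding which one to submit. Someone seeking training might bring a case that went badly, which would make later results look like improvement. Someone else might bring the best-documented success, which would hide improvement. After training there is a similar freedom, because a second supervised case or a later one may be available and nothing says which counts.

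Both arms receive FBT training, so no untrained group would show the same shift and allow it to be subtracted. Whatever selection does to either mean goes into the pre-to-post estimate. The SAP says the results will inform future randomized studies, so a change produced by case choice could be carried forward as a training effect.

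**Working it through.** The documents give no sample size, SD, effect size or caseload for Aim 2, so there is no planned figure to reproduce. What follows shows scale only.

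**Inputs from the documents**
- One baseline case per therapist, from a 6-month look-back or from the alternative route before training (Protocol, eligibility and weight-change item).
- One or two supervised cases, or one in the 3 months after supervision (Protocol, supervision paragraph and weight-change item).
- Baseline assessment completed before randomization (Protocol, baseline procedures).
- Two-sided alpha of 0.05. The SAP states this only for the retention test, and it is assumed here for Aim 2.

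**Assumptions, not in the documents**
- Number of eligible past cases k from 1 to 5.
- Fraction f of therapists who submit their lowest-gain case: 0.25, 0.5 or 1.
- Between-patient SD of session 1 to 4 gain, within therapist: 1 to 2 kg.
- Therapists with both values: n = 10, 20 or 40.
- Normally distributed gains and a true training effect of zero.

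**Step 1: shift from choosing the lowest of k.** With φ and Φ the standard normal density and distribution function,

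E(k) = −∫ x · k · φ(x) · [1 − Φ(x)]^(k−1) dx.

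This gives 0 for k = 1, 0.564 for k = 2, 0.846 for k = 3, 1.029 for k = 4 and 1.163 for k = 5, in SD units. Choosing the highest gives the same values with the opposite sign.

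**Step 2: bias in the mean change.** Bias = f × E(k) × SD.
- f = 0.5, k = 3: 0.5 × 0.846 = 0.423 SD, or about 0.4 kg at SD 1 kg and 0.8 kg at SD 2 kg.
- f = 0.25, k = 3: 0.25 × 0.846 = 0.21 SD, or about 0.2 to 0.4 kg.
- k = 1: 0.

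If a fraction f₁ choose the lowest and f₂ the highest, the bias is (f₁ − f₂) × E(k) × SD, so opposite choices cancel in the mean.

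**Step 3: chance of a false significant improvement.** Paired t-test of post minus pre, 20,000 simulated trials per cell, k = 3, post-training case not selected:

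| Fraction choosing lowest | n = 10 | n = 20 | n = 40 |
|---|---|---|---|
| 0.25 | 6.3% | 9.5% | 15.0% |
| 0.5 | 14.7% | 25.5% | 46.0% |
| 1 | 47.9% | 82.3% | 98.7% |

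With no choice (k = 1) the rate in the direction of improvement is 2.3% to 2.6%, and the two-sided rate is 4.7% to 5.3%.

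**Step 4: both ends open.** If every therapist submits the lower of two cases before training and the higher of two after, the bias is 2 × 0.564 = 1.13 SD.

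**Step 5: between-arm contrast.** With every therapist in both arms submitting the lowest of three baseline cases, the simulated difference in change between arms is about 0 and the two-sided rejection rate is 5.0% (10 per arm) and 5.2% (20 per arm).

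**The case against.** The strongest reply has five parts.

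- **There may be little to choose from.** The Protocol offers an alternative to the look-back, which suggests that some therapists were expected to have no recent case. No caseload figure is given, and with one eligible case there is no baseline bias. This stands as a limit on size. It does not close the gap: the alternative is optional and also has no rule for which case is taken.
- **No motive is built in.** Eligibility sets no weight-gain threshold, and payment is for completed assessments. This stands, and it is why the direction cannot be asserted. A reader might infer that therapists will bring their worst cases and inflate the effect; the documents do not support that. The working assumes a common direction only to show scale.
- **The baseline is not the only end that can be chosen.** A reader might infer that the post-training value is protected because it is collected prospectively. It is not: up to two supervised cases or a later one may be available, with no rule on which counts. Weight change is, however, reported at four weeks for each supervised case, so choice between those two could be settled by a rule in the analysis.
- **The randomized comparison remains.** A reader might infer that all of Aim 2 is compromised. Because the baseline comes before randomization, selection there should be similar in both arms and mainly adds noise. This stands for the baseline. It does not cover choice of the post-training case, which follows allocation, although nothing in the documents suggests that this choice would differ by arm. The Data Analytic Plan describes only the pre-to-post test.
- **Some adjustment is possible.** The baseline survey records how many adolescents with AN were treated in the last two years. That is a coarse proxy for choice in a 6-month window, so it would be too strong to say that nothing could be done in analysis. It is planned only as a candidate predictor.

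The overall aim is feasibility, which lowers the stakes. It does not remove them, since weight gain is the main patient outcome and a significance test is planned on it.

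**Conclusion.** The concern holds for the pre-to-post test in Aim 2. Neither patient in the comparison is fixed by rule, on the look-back route the result is known when the case is chosen, and there is no untrained control. The bias is of unknown direction and unknown amount.

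The 0.42 SD figure rests on assumptions about caseload, the fraction selecting, a common direction and normality, and its conversion to kilograms also needs the assumed SD. The order-statistic values are exact under normality; the absence of a selection rule is a fact of the text.

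A reader might also infer that Aims 3 and 4 inherit the bias because they use the same change in weight gain. A shift in the mean baseline does not by itself bias a correlation of slopes or a predictor's coefficient. That would require selection to be related to change in fidelity or to the predictor, for which the documents give no evidence. Otherwise selection adds noise to those analyses.

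**What to change.** 1. **Protocol, eligibility.** State that the baseline case is the adolescent with AN who started treatment most recently before screening and has the required early weights. On the alternative route, it is the first such adolescent started after screening. The therapist makes no choice.
2. **Protocol, weight-change item.** State that the post-training case for Aim 2 is the first eligible adolescent started after training ends, whether or not a second case is supervised.
3. **Online screen.** Record how many eligible cases the therapist had in the 6-month window.
4. **SAP, Aim 2.** Report the pre-to-post change separately for therapists with one and with more than one eligible case. The first group had no choice on the look-back route, so a marked difference between the groups would be a warning sign, though not proof of selection.

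The cost is a sentence at each of the two places in the Protocol, one screening item and one line in the SAP. The downside is that some therapists must submit a less well documented case, and that compliance with the rule is self-reported.

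### The two supervisors who score the vignettes will know the patient weights and no masking is described, so the Aim 3 correlation for the vignette score may be inflated

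*Protocol*

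**What the plan says.** The Protocol paragraph on UCSF's role gives the same two clinicians several functions. They supervise each therapist weekly for 12 weeks. They also rate: "They will rate fidelity using a therapist version of self-report (described below) and will rate the recorded responses to the" clinical vignettes. On access it says "They will have access to all of the fidelity assessments", and on outcome knowledge "They will also know the patient weight change data (solely session 1 through 4 weights and dates taken". The reason given is "as they need this information to teach the therapist using supervision".

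Under Key component skills, the vignette responses are collected at baseline, at about 3 months (end of training) and at about 6 months (end of supervision), and "will be scored by expert clinicians using standardized coding". Their use is also stated there: "This is a measure of fidelity and change will be correlated with patient weight change outcome (Aim 3) for target validation". The SAP's Aim 3 carries this out in a latent variable model, mainly by correlating the slopes of the clinician and patient outcomes.

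The post-training weight comes from one patient "per participating therapist during supervision or within 3 months following completion of supervision". The baseline patient's weight change is an eligibility item, supplied before training starts.

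Neither document mentions masked scoring, an independent rater, removal of identifiers, random ordering of recordings, or locking of scores before weights are seen. Each therapist is supervised by one of the two clinicians, but nothing says whether that clinician or the other one scores the therapist's recordings.

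**The concern.** Aim 3 asks whether therapists whose FBT skill improved more also had patients who gained more weight. The answer is informative only if the skill score is formed independently of the weight. Here the people who form it know the weight and have spent 12 weeks discussing the case with the therapist. A supervisor who knows that the case went well may score the final recording a little more generously. Such a shift raises the correlation even if skill and outcome are unrelated, and the planned data cannot separate it from a real association.

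The SAP uses this correlation to validate the training effect and as the groundwork for mediation analyses in later randomized studies. An inflated value would carry forward into those designs. Scoring the vignettes does not require the weights; the stated need for them is teaching.

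**Working it through.** The plan gives no sample size, expected correlation or rater-error figure for Aim 3, so there is no figure to reproduce. The calculation shows direction and possible size under stated assumptions.

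**From the documents:** assessments at months 0, 3 and 6; the patient outcome measured once before and once after training; slopes correlated.

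**Assumed:** ratings R0 (baseline) and R2 (end of supervision) and weight gains W0 (pre-training patient) and W1 (post-training patient) all have SD 1; corr(R0, R2) = ρ = 0.5; corr(W0, W1) = c = 0; no true association. The rater shifts R2 by b SD per SD of W1, for a fraction f of therapists whose weight is known at scoring.

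**Step 1, what enters the slope.** Least-squares weights at months 0, 3 and 6 are −1/6, 0 and +1/6. The slope is (R2 − R0)/6, so a shift in the end-of-supervision score alone enters it fully.

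**Step 2, only the end-of-supervision score shifted.** The covariance of rating change with weight-gain change is f·b·(1 − c). The variances are 2(1 − ρ) + f·b² and 2(1 − c). Hence

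r = f·b·(1 − c) / √{[2(1 − ρ) + f·b²] · 2(1 − c)}.

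At b = 0.3: f = 0.5 gives 0.15/√(1.045 × 2) = 0.104; f = 1 gives 0.3/√(1.09 × 2) = 0.203.

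**Step 3, baseline score also shifted, by b·W0, all weights known.** The covariance becomes 2b and the rating-change variance 1 + 2b², so r = 2b/√[(1 + 2b²) × 2]. At b = 0.3 this is 0.6/√(1.18 × 2) = 0.39.

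| b | End of supervision only, half known | End of supervision only, all known | Baseline also shifted by W0, all known |
|---|---|---|---|
| 0.1 | 0.04 | 0.07 | 0.14 |
| 0.2 | 0.07 | 0.14 | 0.27 |
| 0.3 | 0.10 | 0.20 | 0.39 |
| 0.5 | 0.17 | 0.32 | 0.58 |

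**Step 4, equal shift at all time points.** If all of a therapist's recordings are moved by the same b·W1, the term drops out of R2 − R0 and r stays at 0.

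**Step 5, sensitivity.** At b = 0.3 with only the end-of-supervision score shifted, varying ρ from 0 to 0.8 and c from 0 to 0.5 gives r of 0.05 to 0.16 (half known) or 0.10 to 0.30 (all known).

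**Step 6, a real association.** In simulation with all weights known and only the end-of-supervision score shifted, a true correlation of 0.30 is observed as 0.36, 0.42, 0.46 and 0.54 for b = 0.1, 0.2, 0.3 and 0.5. With b = 0 it stays at 0.30.

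These are correlations of observed slopes with complete data, not output of the SAP's latent variable model.

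**The case against.** The strongest reply is that the route is indirect. The vignettes are short scripted scenes with actors, not the patient whose weight is known, and the coding is standardized and aimed at two specific skills. A shift needs a halo effect carried over from another case. No document supports any value of b, and at 0.1 with only the end-of-supervision score exposed the induced correlation is at most 0.07. This stands as a limit on size. Standardized coding constrains a rater but does not mask one.

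Exposure may also be partial. Weights that arrive in the 3 months after supervision may be unknown at scoring, and baseline and end-of-training recordings may be scored before the supervised case's outcome exists. Cross-scoring is not excluded by the text, although read literally both clinicians know the weights. In the other direction, the baseline patient's weight is not ruled out as something the raters see, so the end-of-supervision figures are not an upper bound.

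Three stronger readings are tempting and are not supported:

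- **That the Aim 1 rise in vignette skill is inflated by raters expecting improvement.** Nothing says that raters know the time point of a recording. This is a possibility only.
- **That the Protocol contradicts itself on baseline expert ratings.** The baseline assessment says "skills of FBT using responses to role played videotapes, and expert ratings of fidelity will be collected", while supervisor-reported fidelity is collected only at the end of supervision. The baseline expert rating can be read as the vignette score, which experts assign and the Protocol treats as a fidelity measure.
- **That every fidelity measure has this rater problem.** The multiple-choice knowledge test involves no rater judgement. Therapist self-reports are not scored by the supervisors, but they are made by someone who knows the weight: the fidelity self-report and the weight change are both completed at the 4-week mark of each case. That is a separate route.

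**Conclusion.** The concern holds for the vignette score in Aim 3. It is documented that the supervisors score the vignettes, that they will know the weights, and that change in the score is correlated with weight change. Masking and scorer allocation are not described. The correlation may be inflated; it would go too far to infer that it is inflated or by how much.

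The illustrative range runs from 0.04 (b = 0.1, half the weights known) to 0.32 (b = 0.5, all known) when only the end-of-supervision score is exposed. It is 0.14 to 0.58 if baseline scores are also shifted by the baseline patient's weight, and zero if the shift is equal throughout. All of this rests on the assumed b, f, ρ and c.

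Supervisor-reported fidelity is exposed to the same knowledge but is rated once, so it gives a level and no slope. As this is a feasibility study and only part of one aim is affected, the point is a cheap improvement worth making and does not put the study in doubt.

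**What to change.** 1. Each clinician scores only the vignette recordings of the other clinician's supervisees. Remove therapist identity and arm, and time point where practical. Since baseline recordings may be scored before a supervisor is assigned, whoever scores them should not later supervise that therapist.
2. Set REDCap permissions so that the scorer cannot see those therapists' baseline and post-training weights or self-reports. Each supervisor keeps their own supervisees' weights for teaching.
3. Score and lock baseline and end-of-training recordings before the post-training weight is available. If masking of time point is preferred, score all recordings in one batch in random order. Choose one and write it down: batching gives up scores that could have been made before the outcome existed.
4. In Aim 3, report results by measure, label supervisor-reported fidelity as rated with knowledge of the outcome, and note that therapist self-reports are also made knowing the weight.
5. Separately, reconcile two items on supervisor-rated fidelity. The paragraph on UCSF's role names a version of the self-report as the instrument, while the measure's own description names a published coding frame. That description also refers to change in a rating made only once.

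Cost: no extra raters, visits or assessments. Someone must strip identifiers and coordinate the scoring. Masking will be imperfect, because the two supervisors may confer and a voice or trained FBT language may be recognised.
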